1.1 Study design

This is a 52-week, randomized, double-blind, double-dummy, placebo-controlled, multicenter study to assess the efficacy of secukinumab 150 mg or 300 mg in patients with AxPsA who have had an inadequate response to two different NSAIDs. The study will consist of two treatment periods; a double-blind placebo-controlled period from Baseline to Week 12 followed by a double-blind secukinumab treatment period from Week 12 to Week 52.

The schematic of study design is given in Figure 1.1 below.

Planned number of patients and randomization

A total of 495 patients (165 patients per group) will be recruited to compensate dropouts and protocol violators.

Patient eligibility will be assessed during a maximum screening period of 8-weeks. At Baseline, all patients whose eligibility is confirmed will be randomized in a 1:1:1 ratio to secukinumab 150 mg, secukinumab 300 mg or placebo. At Week 12, patients randomized to placebo at Baseline will be re-randomized (1:1) to active treatment with secukinumab 150 mg or secukinumab 300 mg.

Group 1: secukinumab 150 mg

Treatment Period 1

secukinumab 150 mg (1 × 1.0 mL prefilled syringes (PFS)) + placebo (1 × 1.0 mL PFS) at Baseline, Week 1, 2, 3 and 4, then 4 weeks later at Week 8.

Treatment Period 2

secukinumab 150 mg (1 × 1.0 mL PFS) + placebo (1 × 1.0 mL PFS) administered every 4 weeks from Week 12 to Week 52 (last dose on Week 48).

Group 2: secukinumab 300 mg

Treatment Period 1

secukinumab 300 mg (2 × 1.0 mL PFS) administered at Baseline, Week 1, 2, 3 and 4, then 4 weeks later at Week 8.

Treatment Period 2

secukinumab 300 mg (2 × 1.0 mL PFS) administered every 4 weeks from Week 12 to Week 52 (last dose on Week 48).

Group 3: placebo

Treatment Period 1

placebo (2 × 1.0 mL PFS) administered at Baseline, Week 1, 2, 3 and 4, then 4 weeks later at Week 8.

Treatment Period 2

secukinumab 150 mg (1 × 1.0 mL PFS) + placebo (1 × 1.0 mL PFS) administered every 4 weeks from Week 12 to Week 52 (last dose on Week 48), OR

secukinumab 300 mg (2 × 1.0 mL PFS) administered every 4 weeks from Week 12 to Week 52 (last dose on Week 48).

[figure not shown]
Patients, investigator staff, persons performing the assessments and data analysts will remain blinded to the identity of the treatment from the time of randomization until database lock. No stratification at randomization will be performed.

Primary analysis time point

The primary and key secondary analyses will be performed at Week 12.

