2.1.1 General definitions

Study treatment: Study treatment refers to:

Secukinumab 150 mg provided in 1 ml PFS or Secukinumab placebo provided in 1 ml PFS.

Study treatment start and end date: Study treatment start date is defined as the first date when a non-zero dose of study drug is administered and recorded on the Drug Administration Record (DAR) CRF page. Similarly, study drug end date is defined as the last date when a non-zero dose of study drug is administered and recorded on the DAR CRF page of the core study.

Study day: Study day will be calculated as (event date – study drug start date + 1 day) for events that occurred on or after study drug start date (e.g., visit, lab samples, AEs). For events prior to study drug start date (e.g., time of diagnosis), study day will be negative and calculated as (event date – study drug start date). Note that study drug start date is study day 1 and the day before study drug start date is study day -1 (i.e. no study day 0).

Due to the study drug dosing schedule, one month will be considered as 28 days. However, for “time since event” data (e.g., medical history), one month will be considered as 365.25/12 days for events that occurred prior to study Day 1. Time from events prior to the start of study drug, e.g., time since diagnosis, is calculated as the difference between the start date of study drug and the date of prior event.

Note that, the first dose day is Day 1, and the day before the first dose day is counted as Day -1 (not Day 0).

Baseline and post baseline: In general, a *baseline* value refers to the last measurement made prior to administration of the first dose of study treatment. A post-baseline value refers to a measurement taken after the first dose of study treatment.

Treatment Period: There are 2 treatment periods for this study defined as:

Treatment Period 1 is defined as a 12 Week placebo-controlled, double-blind treatment period starting from baseline till Week 12.

Treatment Period 2 is a 40 Week double-blinded active treatment period starting from Week 12 till Week 52.

Lost to follow up: The patients, whose study completion status is unclear, because they fail to appear for study visits without stating an intention to withdraw.

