2.1.2 Visits windows

Visit-windows will be used for the data that is summarized by visit; they are based on the study evaluation schedule and comprise a set of days around the nominal visit day. For any assessment, there are the protocol defined scheduled visits around which visit windows were created to cover the complete range of days within the study. The visit windows are shown in [Table 2-1](#). These apply to measurements taken at every visit. For assessments, collected less often different visit windows will be applied as detailed below.

When visit windows are used, all visits will be re-aligned, i.e., they will be mapped into one of the visit windows. E.g., if the *Week 4* visit of a subject is delayed and occurs on Day 46 instead of on Day 29, say, it will be re-aligned to visit window *Week 8*. In the case of major deviations from the visit schedule, or due to unscheduled visits, several assessments of a subject may fall in a particular visit window (either scheduled or unscheduled). Statistical approaches to handle multiple assessments in a given visit window are specified below.

Of note, subjects are allowed to have gaps in visits.

Table 2-1 Assessment windows for scheduled visits

Analysis Visit	Week	Scheduled Day	Visit Window
Baseline	BSL	1	-28 days to Day 1*
Week 1	1	8	Day 2-11
Week 2	2	15	Day 12-18
Week 3	3	22	Day 19-25
Week 4	4	29	Day 26-43
Week 8	8	57	Day 44-71
Week 12	12	85	Day 72-104
Week 16	16	113	Day 105-141
Week 24	24	162	Day 142-183
Week 32	32	218	Day 184-253
Week 40	40	289	Day 254-323
Week 48	48	337	Day 324-351
Week 52	52	365	Day 352 onwards

* Baseline measurement before the first drug administration for safety assessments and before the randomization for efficacy assessments. For efficacy visit windows, refer to date of randomization.

For parameters, which are not collected at every visit (e.g., FACIT-Fatigue©, HAQ-DI©), visit windows defined in [Table 2-4](#) will be combined. For example, if a parameter is measured at Week 12 and Week 24 only, Week 12 visit window will extend from Day 2 to Day 104 (combining Week 1 to Week 12 visit windows), Week 24 will extend from Day 105 to Day 183 (combining Week 16 to Week 24). If more than one assessment falls into the interval, the rules defined in [Section 2.1.3](#) below are applied.

Table 2-4a Drug administration windows for scheduled visits of Exposure Data

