2.1.3 Multiple assessments within visit windows

When there are *multiple assessments* in a particular visit window, the following rules are applied to select one value “representing” the subject in summary statistics in a visit window (See [Table 2-2](#)).

For baseline assessment definition, see [Section 2.1.1](#). For post-baseline visit windows, the following applies (unless otherwise specified):

- for *quantitative variables*, the *closest* to the actual visit is chosen (if two assessments have the same distance, then the earlier one will be chosen);
- for *qualitative variables*, the *worst* record is selected. It is noted that in the analyses performed, *worst* case is always well defined.
- in case qualitative variables are based on quantitative variables, e.g. ACR 20 response, the visit will be assigned to the quantitative variable, and this visit will be used for the derived qualitative variable.

Table 2-2 Rules for selecting values for analysis

Timing of measurement	Type of data	Rule
Baseline	All data	
The last non-missing measurement made prior to or on the date of administration of the first dose of study treatment (the reference start date / Day 1). If a patient did not receive any dose of study treatment, then the randomization date will be used. Only date part is considered if just one assessment on Day 1.
 
If there are multiple assessments on Day 1, following rules will apply:
 
a. If assessment time exists,
• select the last available measurement prior to reference start date/time considering time;• if no measurement prior to reference start date/time considering time, select the earliest measurement post reference start date/time considering time.b. If assessment time does not exist, select the available measurement from the lowest CRF visit number.

Timing of measurement	Type of data	Rule
Post-baseline efficacy	All data	
The measurement closest to the target day will be used. In the event two measurements are taken equally apart (e.g., 1 day before target date and 1 day after), the earlier one will be used.
 
Cases where the same parameter is recorded more than once on the same date will be handled as follows:
 
 • If time of completion exists, the earliest measurement will be used; • If time does not exist, the measurement from the lowest CRF visit number will be used.

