2.8 Safety analyses

All the safety analysis will be performed on the Safety set.

Summaries may be performed separately for the initial (Week 1-12) and entire treatment periods.

The analyses of the follow-up period will be limited to summaries for treatment-emergent adverse events, and serious adverse events.

Safety analyses will be performed on treatment received or actual treatment as described below:

The actual treatment or treatment received for summaries of safety data will differ to the treatment assigned at randomization only if a subject received the wrong treatment during the entire study.

For those patients who did not receive the randomized treatment, i.e. who received erroneously the wrong treatment at least once, an additional AE listing will be prepared displaying which events occurred after the treatment errors and also the relationship with study drug.

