2.8.1 Adverse events (AEs)

The crude rates of treatment emergent adverse events (i.e. events started after the first dose of study treatment or events present prior to the first dose of study treatment but increased in severity based on preferred term, and events until 12 weeks after last dose of study treatment) will be summarized by primary system organ class and preferred term.

In addition, exposure time-adjusted incidence rates including 95% confidence intervals will be provided for the entire treatment period to adjust for differences in exposure. A graphical display of the crude rates and exposure-adjusted incidence rates will be presented for all AEs and serious AEs by system organ class.

Adverse events will be summarized by presenting, for each treatment group, the number and percentage of patients having at least one AE, having an AE in each primary system organ class and having each individual AE (preferred term). Summaries (crude rates only) will also be presented for AEs by severity and for study treatment related AEs. If a particular AE 'severity' is missing, this variable will be listed as missing and treated as missing in summaries. If a subject reported more than one adverse event with the same preferred term, the adverse event with the greatest severity will be presented. If a subject reported more than one adverse event within the same primary system organ class, the subject will be counted only once with the greatest severity at the system organ class level, where applicable.

Separate summaries will be provided for

- adverse events suspected to be related to study drug by the investigator
- deaths
- serious adverse events
- adverse events leading to discontinuation
- adverse events leading to temporary dose interruption.
- adverse events of special interest

Adverse events will also be reported separately by SMQ according to MedDRA, using a narrow search. The MedDRA version used for reporting the study will be described in a footnote.

Follow-up period summaries will be done for all patients in follow-up.

A listing of non-treatment emergent adverse events will be done. These adverse events occurred before the first dose of the study treatment. The crude rates will be provided without treatment information.

For SAEs occurred during screening a listing will be prepared for all patients screened including screening failures.

Algorithms for date imputations will be provided in Programming Specifications.

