After Treatment Start	Partial indicates date after Treatment Start Date			
Uncertain	Partial insufficient to determine relationship to Treatment Start Date			
LEGEND:				
(A)	MAX(01MONYYYY,TRTSTD+1)			
(B)	TRTSTD+1			
(C)	15MONYYYY			

(D)	01JULYYYY
(E)	01JANYYYY

AE end date imputation

For the purpose of date imputation, the study treatment follow-up period date is defined as the last available visit date, i.e. including unscheduled visits after the end of study visit.

1. If the AE end date month is missing, the imputed end date should be set to the earliest of the (study treatment follow-up period date, 31DECYYYY, date of death).
2. If the AE end date day is missing, the imputed end date should be set to the earliest of the (study treatment follow-up period date, last day of the month, date of death).
3. If AE year is missing or AE is ongoing, the end date will not be imputed.

If the imputed AE end date is less than the existing AE start date then use AE start date as AE end date.

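### The Week 52 window has no upper limit and there is no follow-up category, so some post-treatment values can be labelled Week 52

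*SAP*

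**What the plan says.** **Windows.** SAP Section 2.1.2, Table 2-1, schedules Week 52 on Day 365 and gives its window as "Day 352 onwards". Every other post-baseline row of that table has an upper limit. The text says that "all visits will be re-aligned, i.e., they will be mapped into one of the visit windows", and it expects unscheduled visits to fall into windows too. No row exists for follow-up.

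**Selection within a window.** Section 2.1.3 takes the quantitative value closest to the target, with the earlier one chosen in a tie. Table 2-2 applies the same rule to all post-baseline efficacy data. For qualitative variables "the *worst* record is selected". A category derived from a quantitative variable follows the choice made for the quantitative variable.

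**End of treatment and follow-up.**
- Section 1.1 puts the "last dose on Week 48".
- Section 2.1.1 says "Treatment Period 2 is a 40 Week double-blinded active treatment period starting from Week 12 till Week 52".
- Section 2.8.1 counts as treatment-emergent "events until 12 weeks after last dose of study treatment".
- Section 2.8 says "The analyses of the follow-up period will be limited to summaries for treatment-emergent adverse events, and serious adverse events".
- Section 5.1.2, in defining a cap for adverse event end dates, refers to the last available visit, "including unscheduled visits after the end of study visit".

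**The concern.** Section 2.1.2 describes windows as spans of days placed about the planned visit day. An interval that never closes is not that. The SAP also recognises a follow-up period and foresees visits after the end-of-study visit, yet gives those records nowhere to go except Week 52.

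Week 52 is the end-of-treatment time point in every arm. The label feeds several by-visit outputs:
- laboratory change from baseline and shift tables (Section 2.8.3);
- ECG variables (Section 2.8.4.1);
- vital signs (Section 2.8.4.2);
- patient-reported outcomes up to Week 52 (Section 2.11).

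The additional longitudinal model in Section 5.6 also runs to Week 52. If the table is programmed as written, some values in these outputs may come from patients well past their last dose. For qualitative data the replacement goes in one direction only, towards the worse record, and has no time limit.

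**Working it through.** **1. Reproduce the table's own figures.** Scheduled day = 7 × week + 1.
- Week 48: 7 × 48 + 1 = 337. Week 52: 7 × 52 + 1 = 365. Both match Table 2-1.
- Midpoint of 337 and 365: (337 + 365)/2 = 351, so Week 52 starts on Day 352. This matches the printed lower bound.

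**2. How far past target a Week 52 value can lie.**
- The last planned dose is at Week 48, Day 337. An on-time Week 52 value comes 365 − 337 = 28 days later.
- The 12-week post-dose adverse event interval ends on Day 337 + 84 = 421, which is 421 − 365 = 56 days past the Week 52 target.
- A value on Day 421, or on any later day, still falls in the Week 52 window.
- Every inner window is finite. Against the printed scheduled days, the longest overrun is Week 32 (253 − 218 = 35 days). Against 7 × week + 1, Week 40 runs 323 − 281 = 42 days.

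**3. Which value is picked for quantitative and efficacy data.** The rule is closest to Day 365, earlier if tied, among values on or after Day 352.

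| Days with a value | Value used for Week 52 |
|---|---|
| 365 and 421 | 365 |
| 365 and 450 | 365 |
| 352 and 379 | 352 |
| 352 and 377 | 377 |
| 351 and 393 | 393 |
| 340 and 421 | 421 |
| 421 only | 421 |

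Days 340 and 351 belong to Week 48, so they do not compete. A late value is used only when no value on or after Day 352 lies nearer to Day 365. For parameters not collected at every visit, Section 2.1.2 merges neighbouring windows. That can move the lower bound earlier and so bring in a competing value, but it leaves the upper end open.

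**4. Which record is picked for qualitative data.** Distance from Day 365 plays no part. Take an on-time record on Day 365 and a worse one on Day 421: the rule takes Day 421. The outputs were checked for where this can happen:
- Urinalysis frequency tables (Section 2.8.3): exposed.
- Laboratory normal/low/high categories: derived from quantitative values, so step 3 governs.
- CTCAE shifts (Section 2.8.3): use the worst result in the treatment phase, not a visit window.
- ECG interpretation (Section 2.8.4.1): uses the worst on-study reading, not the Week 52 window.
- Urine pregnancy results (Section 2.8.3): reported by visit within each treatment period, and Treatment Period 2 stops at Week 52.

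**The case against.** The strongest reply is that the open end is deliberate. Section 2.1.2 wants the windows to cover all days in the study, the exposure window table also ends open, and an open last row keeps genuine but late Week 52 visits. Section 2.8 can then be read as the safeguard: if follow-up analyses cover adverse events only, follow-up laboratory, ECG and vital-sign values are already out of the summaries. In addition, the SAP schedules no such measurements after Week 52, and the wording in Section 5.1.2 serves date imputation only.

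Much of this stands. A reader might infer that follow-up values are generally reported as Week 52. The documents do not support that, because an on-time quantitative or efficacy value is always kept. A reader might also infer a flat contradiction covering efficacy. The limit sits in the safety section, so it bears directly only on safety summaries, and even there it is better called an unreconciled gap. Nor do ECG interpretation or pregnancy results illustrate the worst-record problem, for the reasons in the working.

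What does not stand is that nothing needs changing. Sections 2.1.2 and 2.1.3 are the programming rules, and they contain no instruction to set post-treatment values aside. Followed literally, they give a Day 421 value the Week 52 label. Keeping late Week 52 visits does not require admitting follow-up records as well.

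**Conclusion.** The point holds in a limited form and is minor. As written, Table 2-1 and the mapping rule label post-treatment records as Week 52, which does not fit the limit on follow-up analyses in Section 2.8. The effect is confined to:
- quantitative and efficacy values in patients with no nearer value on or after Day 352;
- purely qualitative by-visit safety data such as urinalysis, where a worse later record replaces the on-time one.

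The size cannot be computed. The SAP does not say which assessments are taken after Week 52 or how many patients would have them, so any patient count would rest on an assumed share.

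A reader might fear for the trial's conclusions. The documents give no ground for that: the primary, key secondary and listed secondary efficacy endpoints are at Week 12, whose window in Table 2-1 closes on Day 104. Comparisons with placebo focus on the first 12 weeks, and later efficacy is descriptive unless otherwise specified.

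**What to change.** Add a rule to Section 2.1.2. Records from the post-treatment follow-up period, and unscheduled records after the end-of-study visit, are not mapped to Week 52 but to a follow-up category that is listed and left out of the Week 52 summaries. A nominal Week 52 visit that takes place late stays in Week 52. The cost is a sentence and one extra category, and no safety information is lost because the late values remain in listings.

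A stated upper bound is one alternative. Weeks 8 and 48 run 13 days before and 14 days after target (57 − 44 = 13 and 71 − 57 = 14; 337 − 324 = 13 and 351 − 337 = 14). The same pattern gives Day 352 to 365 + 14 = 379; strict mirroring gives 365 + 13 = 378. Either figure is a convention. A bound has the small downside that Week 52 visits later than the limit would not be summarised, which the rule based on visit type avoids.

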2.1.3 Multiple assessments within visit windows

When there are *multiple assessments* in a particular visit window, the following rules are applied to select one value “representing” the subject in summary statistics in a visit window (See [Table 2-2](#)).

For baseline assessment definition, see [Section 2.1.1](#). For post-baseline visit windows, the following applies (unless otherwise specified):

- for *quantitative variables*, the *closest* to the actual visit is chosen (if two assessments have the same distance, then the earlier one will be chosen);
- for *qualitative variables*, the *worst* record is selected. It is noted that in the analyses performed, *worst* case is always well defined.
- in case qualitative variables are based on quantitative variables, e.g. ACR 20 response, the visit will be assigned to the quantitative variable, and this visit will be used for the derived qualitative variable.

Table 2-2 Rules for selecting values for analysis

Timing of measurement	Type of data	Rule
Baseline	All data	
The last non-missing measurement made prior to or on the date of administration of the first dose of study treatment (the reference start date / Day 1). If a patient did not receive any dose of study treatment, then the randomization date will be used. Only date part is considered if just one assessment on Day 1.
 
If there are multiple assessments on Day 1, following rules will apply:
 
a. If assessment time exists,
• select the last available measurement prior to reference start date/time considering time;• if no measurement prior to reference start date/time considering time, select the earliest measurement post reference start date/time considering time.b. If assessment time does not exist, select the available measurement from the lowest CRF visit number.

Timing of measurement	Type of data	Rule
Post-baseline efficacy	All data	
The measurement closest to the target day will be used. In the event two measurements are taken equally apart (e.g., 1 day before target date and 1 day after), the earlier one will be used.
 
Cases where the same parameter is recorded more than once on the same date will be handled as follows:
 
 • If time of completion exists, the earliest measurement will be used; • If time does not exist, the measurement from the lowest CRF visit number will be used.

